## 11. Local Recruitment Methods

11.1. Recruitment Process: Participants will be recruited during their consultation appoint at the University of Minnesota Graduate Endodontics clinic. Advertisements will not be publicly posted.

11.2. Identification of Potential Participants: Potential participants will be recruited from the Graduate Endodontics patient population and will be identified on their consultation exam and rightness of fit based on their demographics and tooth morphology and anatomy. Supplemental investigators will make the initial contact and upon participant signage of consent forms will be made known to the primary investigator. Confirmation of participation will be known when the patient signs a consent form.

11.3. Recruitment Materials: After being identified by a member of the research team, the potential participant will be given recruitment material which is a FAQ sheet that they can take home and read should they need more time to consider the invitation to participate.

11.4. Payment: No gifts, payments, compensation, reimbursement, or services without charge will be provided to the participants for participating in the research.

## 12. Withdrawal of Participants

12.1. Withdrawal Circumstances: Should patients have an occurrence that will eliminate their eligibility for root canal therapy, i.e. an unforeseen crack or fracture.

12.2. Withdrawal Procedures: For research in which it is determined to be appropriate to document the withdrawal of a subject, such documentation could specify:

- Documentation of whether the withdrawal of the participant resulted from a decision by the participant or by the investigator, and the reasons for the withdrawal, if known.
- Whether the withdrawal was from all components of the research study or just the primary interventional component.
- Should any participant want to withdraw from procedures, the participant will be debriefed on which arm of the procedure they were assigned to. An offer to complete treatment via other standard treatment options will be extended. Also, following treatment the participant will not be asked to complete the pain scale assessment, but will have the standard 6 month recall to assess healing. The Office of Human Research Protections also recommends that the investigator explain to the participant the importance of obtaining follow-up safety data about the participant. If the participant agrees, research activities involving these other types of participation for which the participant previously gave consent will continue. Should a participant wish to seek treatment elsewhere, a list of possible endodontists will be furnished. Data collection will terminate at the point of withdrawal.

12.3. Termination Procedures: Procedures will be terminated should the patient want to withdraw or if there is a pathological discovery that would deem the tooth in question non-restorable, after treatment has begun. Should a participant wish to seek treatment elsewhere, a list of possible endodontists will be furnished. Should the tooth be deemed non-restorable, referral to the University's Oral & Maxillofacial Surgery graduate clinic will be provided. Data will not be used following termination.

## 13. Risks to Participants

13.1. Foreseeable Risks:

All risks listed below are associated with both arms of the study.

- **Post-operative discomfort or sensitivity:** Recommendation of 600mg ibuprofen or a combination of 600mg ibuprofen plus 1000mg acetaminophen every 6 hours (Mehrinick)
- **Restrictive mouth opening:** Recommendation of home remedies for limited mouth opening and trismus following extended periods of mouth opening.
- **Jaw muscle spasm or cramps:** This risk can be lessened by using post-procedure massages, heat and ice packs, as well as anti-inflammatory analgesics.

- **Temporomandibular joint difficulty:** This risk can be lessened by using post-operative massages, heat and ice packs, as well as anti-inflammatory medicines.
- **Non-healing of the tooth:** Following treatment, the tooth and symptomatology will be monitored for resolution. Should symptoms not resolve, the next phase of treatment (i.e. root end resection) will be discussed with the participant.
- **Damage to restorations:** If a restoration is damaged beyond the investigator's ability to repair, the proper referral will be made.
- **Reaction to local anesthetic:** Correct administration technique and continual evaluation
- **Uncontrollable Bleeding:** All attempts will be made to arrest bleeding. If bleeding cannot be controlled then a  $\text{Ca}(\text{OH})_2$  medicament can be placed in the tooth and temporary restoration material placed. A subsequent appointment will be scheduled.
- **Separation of instruments within root canals:** Every attempt will be made to remove the separated instrument. If it cannot be removed then an attempt will be made to disinfect and obturate beyond it. The participant will be monitored for healing.
- **Over-instrumentation or over-obturation of root canals:** The working length of the canals will be determined by electronic apex locators and verified using periapical radiographs.
- **Numbness or paresthesia:** The local anesthetic agents used to gain anesthesia have relatively low risk of causing numbness or paresthesia.

Risk specific to Gentlewave treatment

- **Increased sensitivity due to backpressure during machine operation:** Profound anesthesia, and adequate access opening preparation to eliminate possible back pressure during operation.

13.2. Reproduction Risks: N/A

13.3. Risks to Others: N/A

## 14. Potential Benefits to Participants

14.1. Potential Benefits: No direct benefit to individual participants, other than necessary root canal treatment

## 15. Statistical Considerations

15.1. Data Analysis: To examine the research question, a two-sample t test will be conducted to determine if mean differences exist on post-operative pain

following treatment with the Gentlewave system and post-operative pain following standard endodontic treatment. Two-sample t test, with a significance level of 0.05, is an appropriate statistical analysis if each of the two samples can be matched on the pain measurements at 6, 24, 72, and 168 hours following the completion of treatment. A linear mixed effects model will be used to compare the groups across time. Also, descriptive statistics will be used for patient demographics and characteristics.

- 15.2. Power Analysis: A sample size of 17 per group will give an 80% power to detect a mean difference between the two groups of 1 standard deviation. This sample size selection and power analysis is based off of previous studies
- 15.3. Statistical Analysis: A two-sample t-test will be used with a significance level of 0.05 for pain measurements recorded at 6, 24, 72, and 168 hours. A linear mixed effects model will be used to compare the groups across time. Also, descriptive statistics will be used for patient demographics and characteristics.
- 15.4. Quality control of the collected data will be overseen by the principal investigator.

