### **3. Study Endpoints/Events/Outcomes**

- 3.1. Primary Endpoint/Event/Outcome: The primary outcome of this study is to determine whether treatment with the Gentlewave system will significantly decrease the occurrence of post-operative pain with endodontic treatment.
- 3.2. Secondary Endpoint(s)/Event(s)/Outcome(s): The secondary outcome is to determine the intensity of pain, should it occur, based on a NRS pain assessment.

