### **Exclusion criteria were:**

- (i) patients under the age of 18 or those incapable of giving informed consent
- (ii) Patient with premolar or molar with a pulpal diagnosis of normal pulp, previously treated, previously initiated and a periapical diagnosis of asymptomatic apical periodontitis or normal apical tissue requiring root canal therapy.
- (iii) teeth with immature apices

- (iv) teeth with apices in the maxillary sinus or those teeth where the apical lesion has eroded the bone of the maxillary sinus floor.
- (v) teeth with internal or external resorption,
- (vi) teeth with carious lesions or deficient crowns that cannot be repaired before accessing the pulp chamber.

Prior to treatment, a diagnostic exam and sensibility testing were performed. Pain data was collected at the time of presentation by having patients indicate their peak pain or discomfort level at the six-hour mark prior to root canal treatment and symptomatic apical periodontitis was confirmed by using percussion testing and a modified occlusal force meter (Occlusal Force-Meter, GM10, Nagaro Keiki, Tokyo, Japan), as demonstrated by Khan (75). The occlusal force meter numerical reading was recorded at maximal bite force prior to feeling pain on the symptomatic tooth and maximal bite force on the contralateral tooth. Pain measurements were made using a 0-100 NRS. The '0' mark represented 'no pain' and the '100' mark represented 'the worst pain imaginable'. There were 39 additional numeric markings between the '0' and '100' marks that patients could choose, and patients were instructed to write in their pain rating if it was not sufficiently represented on the scale. Along with the numeric scale, the surveys included Wong-Baker FACES as well as verbal markers indicating low, mild, moderate, high, and very high pain. For this study, scores in the very high range were considered severe pain. Scores 0-19 represented low pain, 20-39 was mild pain, 40-59 was moderate pain, 60-79 was high pain, and 80-100 was very high or severe pain.

Patients were divided into one of two treatment groups. Each treatment was scheduled for two appointments regardless of experimental group. For both groups, following confirmation of profound anesthesia, a rubber dam was placed in order to isolate the tooth in treatment. Prior to

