### **Statistical Method**

NRS pain scores were compared between treatment groups at each post-operation time point (6, 24, 72, 168 hours) using linear mixed-effects models with fixed effects for treatment, time, treatment-by-time interaction, and pre-operation NRS pain score, and a random effect for participant to account for within-participant correlation of longitudinal measurements.

Categorical NRS pain scores were compared using mixed-effects logistic regression models with fixed effects for treatment, time, treatment-by-time interaction, and pre-operation NRS pain score category, and a random effect for participant. Mechanical allodynia bite force was compared between treatment groups using the two sample t-test. Mechanical allodynia bite force was compared between treated and control teeth within each treatment group, and between visit 1 and visit 2 in treated teeth within each treatment group, using the paired t-test. Age category, sex, pulpal diagnosis, tooth type, and visit 2 NRS pain category were compared between groups using the chi-square test for association. Continuous measures are summarized using means with 95% confidence intervals. Categorical measures are summarized using rates. Analyses were conducted using R version 4.0.3.

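### Arms are compared at four times at 0.05 each with no primary test: the chance of a false difference is about 13–19%, not 5%

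*Protocol*

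**What the plan says.** **Endpoints.** Protocol 3.1: "The primary outcome of this study is to determine whether treatment with the Gentlewave system will significantly decrease the occurrence of post-operative pain". Protocol 3.2: "The secondary outcome is to determine the intensity of pain, should it occur, based on a NRS pain assessment". Occurrence is therefore primary and intensity secondary. No time point and no cut for occurrence is given.

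**Protocol analysis.** Section 15.3: "A two-sample t-test will be used with a significance level of 0.05 for pain measurements recorded at 6, 24, 72, and 168 hours". It continues: "A linear mixed effects model will be used to compare the groups across time". The mixed model is neither primary nor a gate for the t-tests. Section 15.2 bases the sample size on a difference of 1 SD in a mean: "A sample size of 17 per group will give an 80% power to detect a mean difference between the two groups".

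**SAP analysis.** Statistical Method: "NRS pain scores were compared between treatment groups at each post-operation time point (6, 24, 72, 168 hours) using linear mixed-effects models". In parallel: "Categorical NRS pain scores were compared using mixed-effects logistic regression models with fixed effects for treatment, time, treatment-by-time interaction". The pain bands stand just before the treatment description: "Scores 0-19 represented low pain, 20-39 was mild pain, 40-59 was moderate pain". The lowest band includes a score of zero, and no band boundary is named as defining occurrence. The same section also has between-arm and paired t-tests on bite force. No order of testing or adjustment is stated.

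**Which diary.** Protocol 15.1 refers to the hours after treatment is complete. Protocol 5.1 issues the form after the first appointment only, while the Study Summary and 5.2 issue it after both the first and the final one. The SAP describes a take-home form after visit 1 only.

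**The concern.** The aim is confirmatory: to show that Gentlewave significantly decreases pain. With four tests at 0.05 and none designated, a result below 0.05 at any one time could be presented as that decrease. The 5% error rate then applies to each test but not to the trial's main claim.

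The gap is wider than multiplicity. Nothing links an analysis to the declared primary outcome. The t-tests, the linear mixed model and the power calculation all concern mean NRS, which Protocol 3.2 ranks second. The SAP's logistic model comes closest to occurrence but has no stated cut. The unsettled diary adds another choice, and the SAP's account of visit-2 irrigation does not distinguish the arms, so scores after the two visits may not measure the same contrast.

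**Working it through.** **Inputs.** Alpha 0.05 per time, four times, mean difference 1 SD, 17 per group (Protocol 15.2–15.3); 19 per group (SAP, Research Design); 1:1 allocation (Protocol 10.1). Sidedness is not stated, and two-sided is assumed. The correlation between times is not given, so a range is used.

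**1. The plan's own figure.** For a two-sample t-test with n per arm and a difference of d SDs, the noncentrality is d·√(n/2) on 2n − 2 degrees of freedom. For d = 1 and two-sided 0.05:
- n = 16: √8 = 2.83, power 0.781
- n = 17: √8.5 = 2.92, power 0.807

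Seventeen is the smallest n reaching 80%. The figure reproduces, and it supports the two-sided reading. It is power for one test.

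**2. Error rate with independent times.**
- Any false difference: 1 − 0.95⁴ = 1 − 0.8145 = 0.185
- False Gentlewave benefit: 1 − 0.975⁴ = 1 − 0.9037 = 0.096

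**3. Error rate with correlated times.** Simulation under no effect, equicorrelated normal scores, 100,000 runs per cell:

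| Correlation | 0 | 0.3 | 0.5 | 0.7 | 0.9 |
|---|---|---|---|---|---|
| Four t-tests, 17 per arm: any false difference (%) | 18.4 | 17.6 | 15.7 | 13.3 | 9.5 |
| Same: false Gentlewave benefit (%) | 9.6 | 8.8 | 7.9 | 6.7 | 4.8 |
| Random-intercept contrasts, 19 per arm: any false difference (%) | 18.4 | 17.4 | 15.4 | 12.9 | 9.1 |

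The third row mimics the SAP's model in balanced form, with equal variances, Satterthwaite degrees of freedom and no baseline covariate. A participant effect models the correlation; it does not adjust four contrasts. The t-test rates hardly move with arm size: a separate run at correlation 0.5 gave 15.8% with 17 per arm and 15.6% with 75.

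**4. Unequal variances.** If SDs fall over time (25/22/15/10, assumed), the random-intercept model pools them. With 19 per arm and correlation 0.3–0.7, the chance of any false difference is about 18–22%, and the 6-hour test alone has about 14%.

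**5. Power if the four times share alpha** (1 SD at one time; Bonferroni 0.05/4 = 0.0125):

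| Per arm | 17 | 19 | 25 | 50 |
|---|---|---|---|---|
| One test at 0.05 (%) | 81 | 85 | 93 | >99 |
| At 0.0125 (%) | 61 | 67 | 82 | 99 |

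Twenty-five per arm is the Study Summary's 50 per pulp category split 1:1. At 0.0125, 24 per arm restores 80%.

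**The case against.** - **The SAP replaced the t-tests with a mixed model.** It did, but it reads off the same four comparisons, and the interaction term is not used as a gate. The third row of the error table shows that the change cures nothing. That row matches the t-tests only under equal SDs; with falling SDs the error rate is higher.
- **The 19% end needs zero correlation within patients.** This is fair: 13–17% is more realistic for repeated pain scores. Even at 0.9 the rate is about 9%, nearly double nominal.
- **The primary aim is not stated consistently.** Protocol 1.1 pairs occurrence with severity, and the SAP's Research Design adds mechanical allodynia. Testing mean NRS does serve those statements. This stands, and it is why the fix lets the team make mean NRS primary, provided Protocol 3 is changed to say so.
- **The power loss is small if recruitment is large.** At 50 per arm, Bonferroni power for 1 SD is 99%. True, but the error rate is inflated at any size, and the SAP's stated requirement is 19 per arm.
- **The SAP is in the past tense, so prespecification may no longer be possible.** This also stands. It changes the remedy to adjusted and complete reporting, but does not remove the problem. Selective reporting is a risk the plan leaves open, not something it prescribes.

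**Conclusion.** The plan is wrong as written and must be fixed. With correlation 0–0.7 between times, the chance of any false difference is about 13–19% rather than 5%, and of a false Gentlewave benefit about 7–10% rather than 2.5%. These figures rest on two-sided tests, normal scores and an assumed correlation. They count only the four NRS comparisons and leave out the categorical model, the bite-force tests, a second diary and the separate necrotic and vital analyses in Protocol 10.1. The endpoint mismatch needs no assumption: occurrence is primary, and no analysis or power calculation is assigned to it.

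**What to change.** **Change.**
1. In Protocol 15.3 and the SAP, name one primary test at two-sided 0.05 that matches Protocol 3.1: the treatment effect on occurrence of pain from the SAP's mixed logistic model, at one named time or averaged over the four times after visit 1.
2. State the cut that defines occurrence, for example NRS 20 or more, the SAP's own boundary between low and mild.
3. If mean NRS is to be primary instead, amend Protocol 3 to say so.
4. Report the other NRS, categorical and time-specific comparisons as secondary with Holm adjustment, and give the bite-force tests a stated non-primary rank.
5. Reconcile the diary descriptions in the Study Summary, 5.1, 5.2, 15.1 and the SAP.
6. As a safeguard, let the NRS model's variance differ by time.
7. If results are already known, do not present the choice as prespecified. Report all four times with Holm-adjusted p-values.

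**Cost.** Wording and a few lines of R, plus three statistical costs:
- Individual times face a stricter threshold.
- An averaged contrast is weak against an effect at one time only. For 1 SD in mean NRS at 6 hours alone, the averaged effect is 0.25 SD and the variance of a patient's mean is (1 + 3ρ)/4. With 19 per arm and ρ from 0.3 to 0.7, power is 19% down to 14%. With assumed falling SDs (25/23/20/17 or 25/22/15/10) it is 17–32%.
- Occurrence is less sensitive than mean NRS. By exact power of the Pearson chi-square test at one time, 80% needs a drop such as 70% to 26% or 50% to 10% with 19 per arm, or 70% to 33% or 50% to 14% with 25 (control rates assumed). The mixed logistic model itself was not powered, and its fit should be checked at these arm sizes.

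The team should weigh the last cost before deciding to keep occurrence primary.

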## **16. Confidentiality**

- 16.1. Data Security:

- Data access will be limited to the principal and additional investigators. Data will be de-identified including names, geographic subdivisions, all elements of dates (except the year), telephone numbers, fax numbers, electronic mail addresses, social security numbers, medical record numbers, health plan beneficiary numbers, account numbers, certificate/license numbers, and any other unique identifying number, characteristic, or code. Data will be secured on password protected computer consoles and AHC-IS servers and an AHC-IS supported desktop computer.
- AHC-IS Supported Desktop Device #: 20130133

## **17. Provisions to Monitor the Data to Ensure the Safety of Participants**

Although the procedures included within this study is of minimal risk, the program director/ principal investigator will monitor the data integrity and safety of the participants. The principal investigator will ensure that study is conducted, recorded, and reported in accordance with the protocol, standard operating procedures, and applicable regulatory requirements.

- 17.1. Data Integrity Monitoring.

- Because the procedures included within this study are of minimal risk, the program director/ principal investigator will monitor the data integrity, study design, study milestones and study endpoints and outcomes.
- The principal investigator will ensure that study is conducted, recorded, and reported in accordance with the protocol, standard operating procedures, and applicable regulatory requirements.

#### **17.2. Data Safety Monitoring.**

- Oversight of the trial is provided by the Principal Investigator, [name]. Confidentiality throughout the trial will be maintained by the Graduate Endodontics residents.
- A cumulative review of data will be conducted monthly throughout the entirety of the study and data collection. During the review safety data, efficacy data, data accuracy and untoward events will be discussed.
- Safety information will be collected with case report forms and via monthly in-person meetings with the principal investigator.
- [name], the principal investigator and [name] will monitor the data.
- The only condition that should warrant immediate suspension of the study is if the department Gentlewave machine stops functioning properly and is in need of service.

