- For the standard protocol (control) group, following working length determination, all canals will be cleaned and shaped using rotary files to at least a size 20.04 canal size and to within 0.5 to 1 mm short of the apical terminus. Appropriate final canal size will be determined by the clinician treating the patient. Between each file, 5.25% NaOCl will be

used to disinfect and wash the canals of debris. After the canal has been cleaned and shaped to 20.04, sodium hypochlorite will be passively activated using an ultrasonic instrument for 30 seconds per canal. Next, each canal will soak in 17% EDTA for 1 minute, will be rinsed in 5.25% NaOCl, and finally undergo a final rinse of 95% ethanol. Canals will be filled with Ca(OH)2 and a temporary restoration will be placed with a cotton pellet and restorative material of the clinician's choice. All of these steps make up our standard protocol and would be performed whether research is being conducted or not.

- For the Gentlewave treatment group, the standard protocol will be followed until working lengths are determined. Each canal will be shaped to a canal size of 20.04 or 20.06 and to 1mm short of the apical terminus. An occlusal platform will be prepared to allow Gentlewave treatment of the tooth using the Kool-dam material recommended by Sonendo. The Gentlewave system will be held on the tooth by the clinician and will cycle through five minutes of 3% sodium hypochlorite, two minutes of 8% EDTA, and a final rinse of distilled water. Canals will be filled with Ca(OH)2 and a temporary restoration will be placed with a cotton pellet and restorative material of the clinician's choice. If the research were not conducted, these patients would be treated using the standard protocol as above.
- Pain Management: As both arms include standard of care treatment, pain management will be the same recommendation as our standard, non-research related treatment. Recommendations for pain management include: 600mg Ibuprofen every 6 hours for pain. If additional pain relief is needed, patients are instructed to add 500-650mg Acetaminophen every 6 hours. If these medicines are necessary, participants will be instructed to record which medicines were taken, the amount, at which times, and how often. This will be returned along with the NRS pain assessment.

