## 23. Resources Available

23.1. Resources Available:

- The study will be conducted by a student investigator and co-residents, the faculty advisor will be available for assistance should there be any needed. There are also faculty clinicians trained on the usage of the Gentlewave device should any issues arise.
- Patient consultations for treatment occur daily, either through normal treatment scheduling, or through emergency scheduling. These patient pools should contain more than a sufficient number of necessary participants.
- The research treatment, data collection, and data analysis should require no more than 12-15 months.
- The facilities include 9 dental operatories and a surgical suite equipped with all necessary equipment and instruments to perform standard root canal treatment, including dental operating microscopes. There is one Gentlewave machine, with necessary treatment fluids and hand pieces for all research patient cases.
- Should participants have a medical emergency, we have a first aid kit, ambu bag, oxygen, and AED available. As well as a nearby hospital and fast access to emergency responders.
- All Graduate endodontics faculty, residents, and assistants have been trained on how to properly operate and troubleshoot the Gentlewave device. Prior to starting the research, each participating resident will be given verbal and written instruction on the consent process, the protocol for conducting treatment, and which information needs to be collected from each participant.

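### Protocol section 17.2 makes device malfunction the sole ground for immediate suspension, so participant harm is excluded as written

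*Protocol*

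**What the plan says.** The protocol deals with safety oversight in section 17. Its opening paragraph says that the "principal investigator will monitor the data integrity and safety of the participants" and that the study will follow the protocol, operating procedures and regulatory requirements.

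Section 17.2 then sets out three things that matter here:

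- **Frequency.** "A cumulative review of data will be conducted monthly throughout the entirety of the study and data collection".
- **Content.** "During the review safety data, efficacy data, data accuracy and untoward events will be discussed". No threshold, decision or action follows from that discussion.
- **Suspension.** A single ground is given: "only condition that should warrant immediate suspension of the study is if the department Gentlewave machine stops functioning properly and is in need of service".

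Two other places bear on how to read the suspension sentence. Section 23.1 records that "There is one Gentlewave machine, with necessary treatment fluids and hand pieces for all research patient cases". Section 5.2 says of the Gentlewave arm: "If the research were not conducted, these patients would be treated using the standard protocol as above".

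**The concern.** The suspension sentence stands in the safety monitoring section and is worded as an exclusive rule. Taken literally, a serious injury attributable to treatment, with the machine in working order, is not a reason to stop at once. That is the reverse of what a safety section should say.

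The protocol itself describes harms for which an immediate pause could be needed. Section 2.3 lists severe pain, uncontrollable bleeding, swelling, and necrosis of bone and tissue when hypochlorite passes the apex. It describes these for the irrigant in general, not as a Gentlewave effect, but both arms use that irrigant. Section 13.1 adds one risk specific to the device, sensitivity from backpressure.

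A pause would also change care. Gentlewave participants would otherwise get the clinic's standard protocol, so an alternative is at hand. Without a stated ground to pause, further participants could be given the device before the next monthly discussion.

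**Working it through.** **Step 1: look for any harm-based ground for suspending the study.** The claim fails if another provision supplies one.

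| Place | What it covers | Harm-based ground for study suspension? |
|---|---|---|
| Protocol 12.1 to 12.3 | One participant leaving or being stopped: "Procedures will be terminated should the patient want to withdraw or if there is a pathological discovery" making the tooth non-restorable | No; participant level only |
| Protocol 13.1 | List of risks and how each is handled | No |
| Protocol 17 and 17.1 | General monitoring by the principal investigator; compliance with protocol and regulations | No |
| Protocol 17.2, monthly review | Discussion of safety data and untoward events | No; no consequence stated |
| Protocol 17.2, suspension sentence | Machine not working and needing service | No; excludes other grounds |
| Protocol 19.1 | Treatment and billing for injury; participants to tell study doctors promptly | No |
| Protocol 21.1 and 23.1 | Faculty supervision, emergency equipment, one machine | No |
| SAP | Design, treatment and analysis methods | No |

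Grounds for immediate suspension of the study: 1. Grounds based on participant harm: 0.

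**Step 2: check whether the provisions conflict or coexist.** The monthly review does not contradict the suspension sentence, because discussing events is compatible with not suspending at once. The sentence does weaken the review: an event may be discussed, but the protocol's own rule says it is not a reason for an immediate stop. The general compliance clause in section 17 points both ways. It invokes regulatory requirements, and it also requires conduct according to the protocol, which contains this sentence.

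**Step 3: illustrate the exposure between reviews.** The plan gives no figure for this, so there is none to reproduce.

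Inputs:
- Duration of 12 to 15 months (protocol 5.3 and 23.1).
- Allocation 1:1 (protocol 10.1).
- Number of participants *n*: 150 (protocol 10.1), 100 new participants (protocol Study Summary), or 38 (SAP, Research Design).
- Assumptions: even accrual over the whole period, and no action before the next monthly review.

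Gentlewave participants per month = *n* / months / 2.

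| *n* | All participants per month (15 to 12 months) | On Gentlewave per month |
|---|---|---|
| 150 | 150/15 = 10.0 to 150/12 = 12.5 | 5.0 to 6.25 |
| 100 | 100/15 = 6.67 to 100/12 = 8.33 | 3.33 to 4.17 |
| 38 | 38/15 = 2.53 to 38/12 = 3.17 | 1.27 to 1.58 |

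The 12 to 15 months include follow-up and data analysis, so for a given *n* the rate while participants are being treated would be higher. The figures count participants exposed in a full interval. They are not a probability or a count of injuries, which the documents do not give.

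**The case against.** The best defence is that the sentence is operational. With a single machine, a breakdown necessarily halts the experimental arm, and the authors may simply have named the one immediate stop they expected in a study they call minimal risk. On that reading nobody intended to carry on after a serious injury. This is plausible as to intent. It does not change the text, which is exclusive and sits under safety monitoring. If the intent was operational, correcting the sentence takes nothing away from it.

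Second, the duty to meet regulatory requirements might let the investigator or the ethics board act regardless. That is fair, and nothing here says a pause would be unlawful. But the clause is general, names no ground for suspension, and binds the investigator to the protocol as well. Having to rely on outside authority to override a protocol sentence is a reason to correct it.

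Third, information need not wait for the monthly meeting. Participants are told to report injury promptly, and faculty supervise the residents. This stands, and it means the exposure figures describe a full interval without action, not an expected outcome. It does not supply a ground for suspension once the information arrives.

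Fourth, the practical gap is narrow. The device is FDA cleared, it uses 3% NaOCl and 8% EDTA against 5.25% and 17% in the control arm, and most listed risks apply to both arms. The SAP is written in the past tense, and neither document reports an occasion on which the sentence mattered. All of this limits the practical weight of the point and explains why no stopping boundary is requested. It does not justify a rule that leaves harm out.

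**Conclusion.** The concern holds. As written, section 17.2 excludes participant harm as a ground for immediate suspension of the study, and neither the rest of the protocol nor the SAP repairs it. This is a stated rule that gives the wrong result, not a missing detail.

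The conclusion rests on the wording alone. The illustrative exposure of about 1 to 6 additional Gentlewave participants per review interval depends on the accrual and no-action assumptions above and is not a bound. The low end uses the SAP's 38, which is a power requirement and not a recruitment target.

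The finding says nothing about suspension that is decided later, on which the protocol is silent, and it does not affect any endpoint, allocation or analysis. Confidence in the reading of the text is high. The sentence should be corrected on participant-safety grounds even in a study described as minimal risk.

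**What to change.** Replace the suspension sentence in section 17.2 with:

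*Conditions that warrant immediate suspension include malfunction of the Gentlewave machine and any serious treatment-related injury or other safety concern that the principal investigator or the ethics board considers to require it.*

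This keeps the existing ground, removes the exclusivity and says who decides. A numerical stopping boundary or an independent monitoring board is not needed.

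The cost is one sentence in a protocol amendment, with no change to sample size, visits or analysis.
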